6.1.1 Serious Adverse Event Collection and Reporting

Sections 5.6.1 and 5.6.2 in the Investigator Brochure (IB) represent the Reference Safety Information to determine expectedness of serious adverse events for expedited reporting.

Following the subject's written consent to participate in the study, all SAEs, whether related or not related to study drug, must be collected, including those thought to be associated with protocol-specified procedures. All SAEs must be collected that occur during the screening period and up to 30 days after the last apixaban administration or last induction chemotherapy drug.

Following study completion, any SAE thought to be related to study drug or clinical trial procedures should also be reported to the Sponsor.

An SAE report should be completed for any event where doubt exists regarding its status of seriousness. If the investigator believes that an SAE is not related to study drug, but is potentially related to the conditions of the study (such as withdrawal of previous therapy, or a complication of a study procedure), the relationship should be specified in the narrative section of the SAE Report Form.

SAEs, whether related or not related to study drug, and pregnancies must be reported to BMS (or designee) within 24 hours. SAEs must be recorded on the SAE Report Form; pregnancies on a Pregnancy Surveillance Form (electronic or paper forms). When using paper forms, the reports are to be transmitted via email or confirmed facsimile (fax) transmission to:

SAE Email Address: See Contact Information list.

SAE Facsimile Number: See Contact Information list.

For studies capturing SAEs/pregnancies through electronic data capture (EDC), electronic submission is the required method for reporting. The paper forms should be used and submitted immediately, only in the event the electronic system is unavailable for transmission. When paper forms are used, the original paper forms are to remain on site.

SAE Telephone Contact (required for SAE and pregnancy reporting): See Contact Information list. If only limited information is initially available, follow-up reports are required. (Note: Follow-up SAE reports should include the same investigator term(s) initially reported.) If an ongoing SAE changes in its intensity or relationship to study drug or if new information becomes available, a follow-up SAE report should be sent within 24 hours to the BMS (or designee) using the same procedure used for transmitting the initial SAE report. All SAEs should be followed to resolution or stabilization.

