3 INVESTIGATIONAL PLAN

3.1 Study Design and Duration

Children and adolescents with newly diagnosed ALL or lymphoblastic lymphoma (T or B cell) treated with asparaginase will be eligible for this randomized, open-label, study. The subjects on the apixaban arm will receive study drug during approximately 28 days of induction chemotherapy including asparaginase. The study sample size is approximately 500 randomized patients.

Design

The study is designed to compare the effect of prophylactic oral or enteric apixaban versus no systemic anticoagulant during approximately 28 days of induction chemotherapy on the composite endpoint of adjudicated non-fatal deep vein thromboses (DVT, including symptomatic and asymptomatic), pulmonary embolism (PE), and CVST; and VTE-related-death in subjects (1 to < 18 years) with newly diagnosed ALL or lymphoblastic lymphomas (T or B cell), a functioning CVAD and receiving asparaginase during planned 3-4 drug systemic chemotherapy induction.

[figure not shown]
There are four study periods extending up to a maximum total of approximately five weeks in duration:

- a screening period between Day -7 to Day 4 \pm 3 days of planned 3-4 drug systemic induction chemotherapy prior to randomization
- Note: Screening labs done as part of standard of care prior to signing the informed consent can be used to determine eligibility as long as they were obtained within 1 week prior to enrollment
- Day 1 is defined as the first day of planned 3-4 drug systemic induction chemotherapy
- a randomization period occurring between Days 1 to 4 \pm 3 of planned 3-4 drug systemic induction chemotherapy
- a treatment period, starting with the day of randomization, and extending through Day 29 \pm 5 days of planned 3-4 drug systemic induction chemotherapy. Subjects \geq 5 years will be administered either 2.5 mg, 0.5 mg tablets or oral solution as per [Table 1.2-2](#). Subjects < 5 years and < 35 kg will be administered 0.5 mg tablets as per [Figure 3.1-1](#).
- a follow-up period starting the day after the Day 29 \pm 5 days visit.

The study design schematic is presented in the figure below ([Figure 3.1-1](#)).

Figure 3.1-1: Study Design

Definition of Last Visit – the last visit is the follow-up assessment (telephone or office visit) that occurs on Day 35 ± 5 days.

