^a Screening visit can occur up to 14 days prior to randomization. It can also occur at the treatment visit (Day 1 - 4±3) as long as the subject is eligible by medical history, clinical exam, and has the laboratory results back to confirm the inclusive parameters.

Table 5.1-2: Study Procedural Outline ACCL1333 / CV185155					
Procedure	During Treatment Days 7 ± 5 For in-patients only	During Treatment Days 8 ± 5, 15 ± 5, 22 ± 5	End of Treatment Day 29 ± 5 or early drug discontinuation^a	Follow-up Visit Day 35 ± 5	Notes
Concomitant Medication Assessment	X	X	X	X	If done on Day 7 do not need to repeat on Day 8
Safety Assessments					
Targeted Physical Examination	X	X	X		Includes organ systems pertinent to the subject's signs, symptoms, or adverse events, eg, assessment of signs of VTE or bleeding. If done on Day 7 do not need to repeat on Day 8
Vital Signs	X	X	X		Heart rate, BP, respiratory rate and temperature If done on Day 7 do not need to repeat on Day 8
Adverse Events Assessment	X	X	X	X	Collection of SAEs begins after signed consent Collection of non-serious AE begins after randomization
Laboratory Tests: CBC with Platelets, ALT, AST, and direct (conjugated) bilirubin	X	X	X		If done on Day 7 do not need to repeat on Day 8
Laboratory Tests during the LP RBC in the CSF		X	X		RBC in the CSF only taken at investigator defined LPs

Table 5.1-2: Study Procedural Outline ACCL1333 / CV185155					
Procedure	During Treatment Days 7 ± 5 For in-patients only	During Treatment Days 8 ± 5, 15 ± 5, 22 ± 5	End of Treatment Day 29 ± 5 or early drug discontinuationa	Follow-up Visit Day 35 ± 5	Notes
In-patient Pharmacokinetic (PK) and anti-Xa sample collection. See Section 5.5	X				For subjects receiving apixaban only. For inpatient, a pre-dose PK and anti-FXa sample may be taken 1 day prior to LP (prior to the day 7 AM dose if LP on day 8) followed by a PK and anti-FXa sample taken 1-4 hr post dose. If the subject is outpatient, follow alternate sample collection procedures.
Alternate PK sample and anti-Xa collection. See Section 5.5		X			For outpatients, random PK and anti-FXa samples may be obtained prior to LP procedures for example during the Day 8 ± 5 visit and during Day 15 ± 5 visits.
Efficacy Assessments					

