1 BACKGROUND

Research Hypothesis:

Administration of prophylactic apixaban, orally or via a nasogastric or gastric tube (NGT, GT), during induction chemotherapy will reduce the risk of venous thromboembolism (symptomatic + asymptomatic), compared to no systemic anticoagulant prophylaxis, during induction chemotherapy in children with newly diagnosed ALL or lymphoblastic lymphoma (T or B cell) treated with asparaginase.

Schedule of Analyses:

The final analyses for the study will be performed after all subjects either complete the study treatment period followed by a 6-day follow up period, or discontinue prematurely.

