2.1 Study Design

The study is designed to compare the effect of prophylactic apixaban versus no administration of systemic prophylactic anticoagulant during planned 3-4 drug systemic induction chemotherapy, on the composite endpoint of adjudicated non-fatal asymptomatic and symptomatic VTE and VTE-related death during approximately 28 days of open-label treatment in subjects (1 to <18 years) with newly diagnosed ALL or lymphoblastic lymphomas (T or B cell), a functioning CVAD and receiving asparaginase during planned 3-4 drug systemic chemotherapy induction.

- There are four study periods extending up to maximum total of approximately five weeks in duration:
- a screening period, between Day -7 to Day 4 \pm 3 days of planned 3-4 drug systemic induction chemotherapy prior to randomization
- a randomization period occurring between Days 1 to 4 \pm 3 of planned 3-4 drug systemic induction chemotherapy
- a treatment period, starting with the day of randomization, and extending through Day 29 \pm 5 days of planned 3-4 drug systemic induction chemotherapy. Subjects \geq 5 years will be administered either 2.5-mg, 0.5-mg tablets or oral solution, use of 2.5-mg or 0.5-mg tablets is encouraged. Subjects <5 years and <35 kg may be administered 0.5 mg tablets only Switching formulations during the course of the study is not encouraged but is allowed.
- a 6 - day (\pm 5 days) follow-up period starting the day after the Day 29 \pm 5 days of 3-4 drug systemic induction chemotherapy

[figure not shown]
Subjects 1 to <18 years of age will be administered apixaban twice daily by mouth or via a NGT or GT according to weight range as per [Figure 2.1-1](#).

Table 2.1-1: Apixaban Doses for Ages 1-18 Years of Age

Weight range	Dose
≥35 kg	2.5 mg twice daily
<35 to 25 kg	2 mg twice daily
<25 to 18 kg	1.5 mg twice daily
<18 to 10.5 kg	1 mg twice daily
<10.5 to 6 kg	0.5 mg twice daily

The study design schematic is presented in Figure 2.1-1.

Figure 2.1-1: CV185155 Study Schematic

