6 STUDY PERIODS, TREATMENT REGIMENS AND POPULATIONS FOR ANALYSES

6.1 Study Periods

The term “**Intended Treatment Period**” will refer to the period from day of randomization through Day 29 visit. This period will be the basis for the summaries of efficacy.

The term “**Treatment Period**” will refer to the period from the day of randomization through the end of treatment Day 29 visit or early discontinuation from study (whichever comes first).

The term “**On-treatment Period**” will refer to the period from the day of first dose through the last dose of study medication. This period will be the basis for the summaries of apixaban safety only, because only the apixaban arm will have dose information.

The term “**Follow-up Period**” will refer to the period starting the day after the Day 29 visit or early discontinuation to Day 35 days visit.

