7.6 Safety

Safety presentations will be based on the Safety Population during the Treatment Period. In addition to the analyses and summaries based on the Treatment Period, the analyses and summaries for bleeding outcomes, AEs, SAEs, SAEs with death outcome, AEs leading to discontinuation, events of special interest, elevations in liver function tests (LFTs), and decreases in platelet counts will also be performed based on the On-Treatment period for apixaban treated subjects only.

For analyses of events during the Treatment Period, non-serious adverse events will be included in analyses if their onset occurs during the Treatment Period, or within 2 days after the end of the Treatment Period. Serious adverse events will be included in analyses if their onset occurs during the Treatment Period, or within 30 days after the end of the Treatment Period. For analyses of events during the On-treatment Period, events will be included if they occur during the On-treatment period, or within 2 days (non SAE) or 30 days (SAE) after the end of the On-treatment period. All events will be listed.

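### SAEs are counted to 30 days after the Treatment Period, but the collection end date is ambiguous, no contact is scheduled after Day 35 ± 5, and the final analysis may start before the window closes

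*Protocol*

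**What the plan says.** Four rules bear on how long SAEs are followed.

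- **Collection.** Protocol 6.1.1 requires all SAEs after consent, related or not, to be collected "up to 30 days after the last apixaban administration or last induction chemotherapy drug". It does not say that the later date governs, or which date belongs to which arm.
- **Counting.** SAP 7.6: "Serious adverse events will be included in analyses if their onset occurs during the Treatment Period, or within 30 days after the end of" that same period. SAP 6.1 runs it from randomization "through the end of treatment Day 29 visit or early discontinuation from study (whichever comes first"). The discontinuation meant there is from the study, not from the drug, so the definition is the same in both arms.
- **Contact.** Protocol 3.1 says that "the last visit is the follow-up assessment (telephone or office visit) that occurs on Day 35" ± 5, and Table 5.1-2 schedules nothing later. The preceding column of that table is "End of Treatment Day 29 ± 5 or early drug discontinuation".
- **Analysis.** SAP 1: "The final analyses for the study will be performed after all subjects either complete the study treatment period followed by a 6-day follow up period". Children who leave early are the other case.

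**The concern.** The SAP counts over one window and the protocol collects over another. SAE tables are counts and percentages of subjects (SAP 7.6.2), so an event on a counted day that nobody collected looks the same as no event.

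The mismatch could fall unevenly. A control has no apixaban date and can only be followed from the last chemotherapy drug. An apixaban child has two candidate dates. Protocol 3.5 requires apixaban to stop for major bleeding, for a thromboembolic event, and for any adverse event that makes continuing contrary to the child's interest. Early stopping is therefore informative, and the children most likely to have been harmed could have the shortest collection window.

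After the Day 35 contact nothing in the schedule prompts a site to ask. In an open-label trial, reporting that is not prompted can differ by arm. At stake are the all-cause SAE and death comparisons.

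**Working it through.** **Inputs.** End-of-treatment visit V: Day 29 ± 5, so Day 24 to 34 (Protocol Table 5.1-2). Last contact F: Day 35 ± 5, so Day 30 to 40 (Protocol 3.1). F comes after V, because follow-up starts the day after the visit. Last induction drug C in the Appendix 12 example: Day 22 (vincristine and daunorubicin, the last systemic drugs under 10 years), Day 28 (prednisone, 10 years and over) or Day 29 (intrathecal methotrexate). Sample size about 500 and trial duration about 6 years (Protocol 3.1).

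**1. The plan's own figure.** 35 − 29 = 6 days, which agrees with the follow-up period in SAP 1 and SAP 2.1.

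**2. End of counting, V + 30.** Nominal 29 + 30 = Day 59. Range 24 + 30 = Day 54 to 34 + 30 = Day 64. For a child who leaves the study early it is 30 days after that date.

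**3. Counted days after the last contact, V + 30 − F.** Nominal 59 − 35 = 24 of 30 days (80%). Smallest: visit Day 24, contact Day 40, 54 − 40 = 14. Largest: contact the day after the visit, for example visit Day 34 and contact Day 35, 64 − 35 = 29.

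**4. Collection by arm if each arm uses its own drug.** An apixaban child who stops on Day S is collected to S + 30. A control is collected to C + 30, that is Day 52, 58 or 59. The control window is longer by C − S:

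| Apixaban stops (S) | Collected to | C = 22 | C = 28 | C = 29 |
|---|---|---|---|---|
| Day 5 | Day 35 | 17 | 23 | 24 |
| Day 10 | Day 40 | 12 | 18 | 19 |
| Day 20 | Day 50 | 2 | 8 | 9 |
| Day 28 | Day 58 | −6 | 0 | 1 |

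For the Day 10 stopper, collection ends 59 − 40 = 19 days before nominal counting ends. If the later of the two dates governs, an early stopper is also collected to C + 30 and the difference is 0.

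**5. Children with an open window at the earliest final analysis.** Assuming uniform accrual, 500 / (6 × 365.25) = 0.228 per day. Over the nominal 24 days that is 0.228 × 24 = 5.5 children. At half or double that rate it is 2.7 or 11.0.

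**The case against.** **One rule for everyone.** Protocol 6.1.1 does not distinguish arms, and apixaban children also receive induction chemotherapy. Read inclusively, collection lasts until both dates have passed. Protocol 3.6 also keeps children who stop study treatment in follow-up for SAE data. For completers, a last dose on Day 28 or 29 gives Day 58 or 59, within a day of nominal counting. The inclusive reading is possible and would remove the arm difference for early stoppers, but the text does not state it. Protocol 3.6 refers to Section 5, whose schedule ends at Day 35 ± 5, and gives no end date for new SAEs. The last-apixaban date is also a reasonable choice for a site, since SAP 7.6 uses it for the on-treatment summaries of apixaban-treated children.

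**Collection is mandatory.** A reader might infer that nothing is collected after Day 35. That is wrong: 6.1.1 requires collection, with reporting within 24 hours. What is missing is a scheduled prompt.

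**Overlapping windows.** Day 35 − 5 is Day 30 and Day 29 + 5 is Day 34, so a reader might infer that the last contact can precede the end-of-treatment visit, leaving up to 34 days uncovered. The documents do not allow this. SAP 2.1 has a "follow-up period starting the day after the Day 29" ± 5, and Protocol 3.1 starts follow-up the day after that visit. The maximum is 29 days.

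**The final analysis.** SAP 1 sets an earliest time, not a lock date, and the End of Study definition in Protocol 3.1 extends to receipt of the last data required for analysis. This eases the problem, and few children are involved. SAP 1 does not refer to that definition, so the inconsistency with SAP 7.6 remains, but it is the weakest part of the point.

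**Conclusion.** The mismatch is real. Counting runs to nominal Day 59 (Day 54 to 64), the collection rule has no clear end date, and nominally 24 of the 30 counted days (14 to 29) follow the last scheduled contact. SAE and death tables can be incomplete and unevenly ascertained by arm.

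The arm difference is conditional. It is 12 to 19 days for a Day 10 stop if sites use last apixaban in that arm, and 0 if the later date was meant. The Day 10 stop is illustrative, Appendix 12 is one regimen, and the documents give no rate of early stopping, so no total across the trial can be stated.

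Two stronger inferences are not supported:

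- That the SAE comparison is biased in a known direction. If only systemic drugs count, a control under 10 years ends at Day 52 and an apixaban completer at Day 58 or 59, so the order reverses.
- That the bleeding endpoints are compromised. SAP 7.6.1.1 analyses major bleeding, and its composite with clinically relevant non-major bleeding, during the treatment period.

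**What to change.** - **Protocol 6.1.1:** state one end date for SAE collection in both arms, whenever apixaban stopped. It should be 30 days after the latest of the Day 29 ± 5 end-of-treatment visit (or early discontinuation from study), the last apixaban dose and the last induction chemotherapy drug. Say that the site closes this date by record review, with no extra visit.
- **SAP 7.6:** keep the counting window the same in both arms.
- **SAP 1:** have the final analysis follow closure of the last child's 30-day SAE window.

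The visit alone is not enough as the anchor. With a visit on Day 24 and a last drug on Day 29 it would end collection at Day 54 instead of Day 59, and it gives no date for children who leave the study before the visit. With the latest of the three dates, required collection never ends before SAP counting does.

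The cost is wording in two documents, one record review per child, and a database lock up to about 4 weeks later (24 days nominally and at most 29, from step 3).

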6.2 Non-serious Adverse Events

A *nonserious adverse event* is an AE not classified as serious.

6.2.1 Nonserious Adverse Event Collection and Reporting

The collection of nonserious AE information should begin at randomization for all patients, including the patients randomized to the usual care arm.

Nonserious AEs should be followed to resolution or stabilization, or reported as SAEs if they become serious (see [Section 6.1.1](#)). Follow-up is also required for nonserious AEs that cause interruption or discontinuation of study drug, or those that are present at the end of study treatment as appropriate. All identified nonserious AEs must be recorded and described on the nonserious AE page of the CRF (paper or electronic). Completion of supplemental CRFs may be requested for AEs and/or laboratory abnormalities that are reported/identified during the course of the study.

6.3 Laboratory Test Result Abnormalities

In order for BMS to collect additional information about clinically important laboratory abnormalities, at a minimum, the following laboratory test results abnormalities should be captured on the non-serious or serious AE report pages of the CRF (paper or electronic) as appropriate:

- Any laboratory test result that is clinically significant or meets the definition of an SAE
- Any laboratory test result abnormality that required the subject to have study drug discontinued or interrupted
- Any laboratory test result abnormality that required the subject to receive specific corrective therapy such as platelet transfusions in order to keep platelets $\geq 20 \times 10^9$ per L or to treat bleeding episodes. Blood transfusion to correct anemia secondary to bleeding. Plasma infusions to correct bleeding complications.

It is expected that wherever possible, the clinical rather than laboratory term would be used by the reporting investigator (eg, anemia versus low hemoglobin value).

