3.4.2 Other Restrictions and Precautions

Based on pre-clinical and clinical data, apixaban might increase the likelihood of bleeding. Hence, subjects with platelet counts < 20,000 /microL, undergoing a lumbar puncture, or having surgical procedures, including a bone marrow aspirate and dental procedures should be instructed to inform their doctors about these procedures, and proper cautions should be taken by the investigator to reduce potential risk of bleeding (see [Section 4.5.2](#) for instruction).

Apixaban should not be administered if the platelet count is < 20,000/ microL. A subject may be transfused platelets per investigator's clinical judgement but may not be transfused solely to meet entry criteria.

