Scheduled surgical procedures	
If a subject participating in the study requires an elective procedure or surgery, the following considerations should be taken into account: The effective half-life of apixaban when administered twice daily is approximately 12 hours and it is expected that most of the anticoagulation effect will be gone within 24 hours after the last dose of the drug. Apixaban must be stopped for a sufficient period of time (eg, at least 24 hours if low risk of bleeding and at least 48 hours for moderate or high risk of bleeding) prior to the procedure to minimize the risk of anticoagulant-related bleeding. The treating physician should be made aware of the time and dosage of apixaban administration and be informed that routine coagulation tests such as INR/PT and aPTT are relatively insensitive measures of anticoagulation activity and are unsuitable for monitoring the anticoagulation effect of apixaban. The subject will re-start study medication once hemostasis is secure and when, in the opinion of the investigator, it is safe to do so.

Thrombocytopenia. An AE/SAE should be reported if applicable	
A platelet count should be $\geq 20 \times 10^9$ per L within 24 hours of starting apixaban. There are no evidence-based guidelines for anticoagulation therapy in relation to platelet counts. In absence of any other coagulopathy, following guidelines are recommended during the course of the study period:
 
 • Full-dose apixaban therapy for patients with platelet count $\geq 20 \times 10^9$ per L. • Withhold apixaban for platelet count $< 20 \times 10^9$ per L. Platelet transfusions can be given per the investigator's clinical judgement. 
It is important to maximize thromboprophylaxis therapy. In some circumstances, physicians may choose to give platelet transfusions prior to anticoagulation to maximize anticoagulation exposure in patients with thrombocytopenia. Close monitoring of platelet count and careful watching for signs of bleeding are necessary. Depending on anticipated drop in platelet count, the platelet counts should be checked at least twice a week and

Table 4.5.2-1: Temporary Dose Interruptions for Apixaban

Event	Apixaban
	apixaban should be re-started only after platelets are $\geq 20 \times 10^9$ per L OR after a platelet transfusion that is predicted to increase the platelet count to this threshold according to clinical judgment.

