7.6.2 Adverse Events

All AEs will be coded and grouped into Preferred Terms (PT) by System Organ Class (SOC), using the Medical Dictionary for Regulatory Activities (MedDRA). Listings and summaries will be based on the resulting SOCs and PTs.

The incidence of bleeding-related AEs during the Treatment Period will be summarized by SOC, PT and treatment group.

All reported AEs and SAEs will be listed, indicating the subject id, treatment group, age, gender, race, day of onset relative to start of dosing, resolution date, investigator-assessment of relationship to study drug, investigator-assessment of intensity of event, action taken regarding study drug and whether treatment was required for the event.

Summary information (the number and percentage of subjects) regarding AEs (for serious and non-serious events) will be tabulated by SOC, PT and treatment group for:

- all events
- deaths
- related events
- all events categorized by intensity

The frequency of subjects discontinuing study drug due to AEs will be tabulated by SOC, PT and treatment group.

Most common AEs (reported in more than 5% of subjects in any treatment group) will also be summarized by PT and treatment group.

Laboratory AEs are laboratory results identified by the Investigator as AEs and thus reported on the AE pages of the CRF. Any such AE occurring during the Treatment Period will be included in the respective AE summaries.

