- decreases will be counted if they occur during the Treatment Period; only platelet counts that meet the criteria and are smaller than the baseline count will be included in the tabulations. If baseline value is missing then all platelet counts that meet the criteria will be included in the tabulations
- for each subject, the smallest platelet count obtained during the Treatment Period will be counted for the Treatment Period summaries that do not take nominal visit into consideration
- for each subject, the smallest platelet count obtained within each visit window during the Treatment Period will be counted for the summaries by nominal visit.

[figure not shown]

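### Holding study drug is a trigger for recording a laboratory AE that only the apixaban arm can meet, so thrombocytopenia AE rates, and to a lesser extent liver-test AE rates, can be inflated on apixaban with no drug effect.

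*Protocol*

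**What the plan says.** Protocol 6.3 states that, at a minimum, "the following laboratory test results abnormalities should be captured on the non-serious or serious AE report pages of the CRF". Three triggers follow:

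- a clinical or seriousness trigger, worded as "Any laboratory test result that is clinically significant or meets the definition of an SAE";
- a study-drug trigger, worded as "Any laboratory test result abnormality that required the subject to have study drug discontinued or interrupted";
- an abnormality that needed "specific corrective therapy such as platelet transfusions in order to keep platelets" at or above 20 x 10^9/L, or similar treatment.

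The first and third can be met in either arm. The second needs a study drug, and SAP 6.1 notes that dose information exists only for apixaban. Protocol 6.2.1 has non-serious AEs collected from randomization in the usual-care arm as well.

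The second trigger is tied to foreseeable events. Protocol 3.4.2 says "Apixaban should not be administered if the platelet count is < 20,000/ microL", and Protocol 6.6 requires stopping for confirmed marked liver-test elevations. The thrombocytopenia and liver rows of Table 4.5.2-1, which governs apixaban interruptions, each add a reminder to report an AE or SAE where applicable. For thrombocytopenia the same table says "the platelet counts should be checked at least twice a week", depending on the anticipated fall. Protocol 5.3.7 repeats this for subjects below, or expected to fall below, 20 x 10^9/L and links it to restarting apixaban.

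In the SAP, 7.6.2 says "Summary information (the number and percentage of subjects) regarding AEs (for serious and non-serious events) will be tabulated by SOC, PT and treatment group", and laboratory AEs go into those summaries. SAP 7.6.3 separately tabulates measured platelet counts below 20,000 and liver-test elevations by arm. For platelets, "for each subject, the smallest platelet count obtained during the Treatment Period will be counted" in the overall table, and the smallest count in each visit window is used in the by-visit table.

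**The concern.** Two children, one per arm, have the same platelet count of 15,000. If apixaban is held, the first child's result meets a listed trigger for an AE record. The second child's result is recorded only if the investigator calls it clinically significant or treats it. Section 6.3 gives no numeric meaning to clinically significant, and the investigator knows the arm.

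The AE tables then set the two arms side by side as if the capture rule were the same. A difference in thrombocytopenia AEs could come from the recording rule, and no planned analysis would show that. At stake is the comparative AE profile, including the table of AEs reported in more than 5% of subjects in any arm.

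**Working it through.** The documents state no figure on this point, so there is nothing to reproduce. The size below is an illustration.

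**1. Recording rule.** Define:

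- t: true share with the abnormality, set equal in both arms;
- c: share of those recorded through the two triggers open to both arms;
- h: share of abnormal apixaban subjects whose drug is held, taken as independent of c.

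None of these is in the documents.

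Control AE rate = t x c. Apixaban AE rate = t x [c + (1-c) x h]. Hence RR = 1 + h(1-c)/c, which does not depend on t and cannot fall below 1.

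| c | RR, h = 0.5 | RR, h = 0.9 | Rates at t = 30%, h = 0.9 (apixaban vs control) | Difference |
|---|---|---|---|---|
| 1.0 | 1.00 | 1.00 | 30.0% vs 30.0% | 0 points |
| 0.9 | 1.06 | 1.10 | 29.7% vs 27.0% | 2.7 points |
| 0.7 | 1.21 | 1.39 | 29.1% vs 21.0% | 8.1 points |
| 0.5 | 1.50 | 1.90 | 28.5% vs 15.0% | 13.5 points |

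Example for c = 0.5, h = 0.9: 1 + 0.9 x 0.5/0.5 = 1.90.

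If interruption-only records are left out, the apixaban rate becomes t x c and RR returns to 1.00. This assumes that c is the same in both arms. Table 4.5.2-1 allows platelet transfusion ahead of dosing to preserve anticoagulant exposure, so the corrective-therapy trigger may be met somewhat more often on apixaban.

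**2. Do the measured-value tables in SAP 7.6.3 give an independent check?** They do not use the AE triggers, so the answer depends on how often each arm is tested.

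- *Liver tests.* Scheduled tests carry no arm restriction. The repeat and weekly tests in Protocol 6.6 start only after a threshold is crossed and are worded for any subject. The tables are a good check.
- *Platelets.* The common schedule gives about four counts (Day 7 or 8, then 15, 22 and 29). The twice-weekly counts are tied to apixaban. Those taken after a first value below 20,000 cannot add a subject to the overall table, because each subject contributes one smallest count. Those taken because a fall is anticipated can.

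For the second kind, let q be the chance that any one count is below 20,000, with independent counts, and let a share s of apixaban subjects have 8 counts instead of 4. With a = 1-(1-q)^4 and b = 1-(1-q)^8, RR = [s x b + (1-s) x a]/a.

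| q | a | b | RR, s = 25% | RR, s = 50% |
|---|---|---|---|---|
| 2% | 0.078 | 0.149 | 1.23 | 1.46 |
| 5% | 0.185 | 0.337 | 1.20 | 1.41 |
| 10% | 0.344 | 0.570 | 1.16 | 1.33 |

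These values assume that controls have only the scheduled counts. Standard-of-care counts in controls would narrow the gap, and so would positive correlation between successive counts in one child. For platelets the check is only partial.

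**The case against.** The strongest reply is that this is a caveat on descriptive, non-adjudicated tables in an open-label trial. Several parts of it stand.

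- A reader might infer that apixaban rates are inflated by rule. The text says that these abnormalities should be captured, and two of the three triggers apply to both arms. A transfused control qualifies, and Protocol 6.2.1 asks for all identified non-serious AEs in usual care too. At c = 1 there is no bias.
- A reader might infer that the trial could report a significant excess. SAP 7.6.2 and 7.6.3 plan counts and percentages, with no test. Nominal safety p-values are planned only for bleeding.
- A reader might infer damage to the primary safety objective. That endpoint is major bleeding adjudicated by a blinded committee, and it does not use section 6.3.
- The liver side is weaker. One ALT at 10 x ULN leads to a repeat test, and stopping is required if the repeat still exceeds the limit or there is clinical jaundice. Protocol 6.1 also treats potential drug-induced liver injury as an important medical event, which gives marked elevations a route to recording in either arm, although its application to controls could be clearer.
- It would be wrong to assume that every apixaban child has twice-weekly counts. The guidance covers those below, or expected to fall below, the threshold.
- Nor can h be taken as 1. A note in Protocol 4.5.2 leaves interruption below 20,000 to the clinician, while 3.4.2 says not to administer. Those passages need reconciling; no view is taken here on which is right.

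What the reply does not remove is the asymmetry itself. The AE listing shows the action taken on study drug, but not whether another trigger also applied, so the tables cannot be corrected afterwards from that field alone.

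**Conclusion.** The concern holds in a limited form. The capture rule is unequal, the inequality can only raise the apixaban rate or leave it unchanged, and the planned AE tables do not expose it. It bears mainly on thrombocytopenia AEs and less on liver-test AEs.

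The size cannot be fixed from the documents. Over the assumed range the spurious RR runs from 1.00, when the neutral triggers catch everything, to 1.90 at c = 0.5 and h = 0.9. The larger values need investigators to leave about half of control cases unrecorded, which is an assumption.

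The documents do not support a claim of certain inflation, of a significant AE finding, or of any effect on adjudicated major bleeding or the primary efficacy endpoint. The change is still worth making, because it is cheap and protects the comparative AE profile.

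**What to change.** **Protocol 6.3 and CRF guidance.** Keep recording drug interruption. Add AE-capture criteria that apply equally to both arms, using cut-offs already in the protocol: platelets < 20 x 10^9/L, ALT/AST >= 10 x ULN, direct bilirubin > 3 x ULN. Record on the CRF which trigger or triggers led to each laboratory AE.

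**SAP 7.6.2.** Add a by-arm table of laboratory AEs that excludes records made only because study drug was stopped or held.

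**SAP 7.6.3.** Keep the smallest-count platelet table, since replacing it would give up sensitivity to real falls. Add a sensitivity table of platelets < 20,000 using the scheduled-visit value closest to the target day, a selection rule that SAP 8.4 already sets out for changes from baseline.

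**Cost.** Some wording, one CRF field, two extra tables, and somewhat more laboratory AEs recorded in the control arm. The criteria concern recording only; no dosing or clinical management rule changes.
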